The pragmatic trial design selected for the BOTTOMLINE-CS trial is rooted in its focus on evaluating the effectiveness of multisite tissue oxygen saturation monitoring in a real-world clinical setting. This approach emphasizes the applicability of the trial outcomes to typical clinical scenarios by ensuring that the study conditions closely mimic everyday practice. Unlike explanatory trials, which often employ strict participant selection and controlled conditions to determine efficacy under ideal circumstances, a pragmatic trial embraces broader eligibility criteria and diversity in participant characteristics, mirroring the variability seen in daily medical care. Furthermore, the implementation of interventions and monitoring within the usual care processes enables the assessment of the intervention's practical impact, including its feasibility, adherence, and overall utility in routine clinical workflows. The findings from such a pragmatic study are likely to be generalizable and thus informed clinical decision-making.

Sample Size Determination

The following paragraph was from the original protocol registered before the start of the trial. "We assume that the incidence of the composite 30-day complication in the regular care group will be 30% versus 24% in the multisite tissue oxygenation-guided perioperative care group, a 20% relative reduction representing a clinically meaningful and important treatment difference. Based on one-sided Z-test group sequential testing with 3 stages (two interim analyses) and boundary values calculated from O'Brien-Fleming Analog alpha (efficacy) and non-binding beta spending (futility) functions, a total of 927 patients will provide 80% power for detecting a 6% absolute reduction from 30% to 24% at a target alpha-level of 0.05. We plan to recruit 980 patients per group considering a potential ~5% of patients who drop out or have missing data."

Interim Analysis

The following is from the original protocol established before the start of the trial.

"For the interim analyses, O'Brien-Fleming Analog alpha and beta spending functions are used (Table 1, Figure 1). Assuming two interim analyses occur after 33% and 67% of total patients are enrolled and their primary outcome are observed, the nominal alpha levels to reject the null hypothesis for efficacy or fail to reject the null hypothesis for futility are calculated as follows.

Table 1. Critical values and alpha levels for two interim analyses and final analysis

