Stage	Target Information (%)	N1	N2	Efficacy Boundary (Critical Z-value scale)	Alpha Spent	Futility Boundary	Beta Spent	Power
1	33%	309	309	±3.710	0.0002		0	-

[figure not shown]
2	67%	618	618	± 2.511	0.0119	± 1.157	0.0828	-
3 (final)	100%	927	927	± 1.932	0.0379	± 1.932	0.1172	0.803

Note: O'Brien-Fleming Analog alpha and beta spending function is adopted

The trial could be stopped for efficacy if the efficacy boundary is crossed at first ($Z < -3.71$, $\alpha < 0.0002$) or second ($Z < -2.51$, $\alpha < 0.0119$) interim analysis, respectively (Figure 1). We will evaluate the combined outcome incidence at the first intermediate analysis and increase sample size at that point if it proves to be lower than anticipated.

If the futility boundary is not crossed ($-1.16 < Z < 1.16$) at second interim analysis, and the study will continue if there is no safety concern. If needed, the sample size of the study might be re-estimated by the DSMB statistician using the observed aggregated data (not the treatment effect) using the conditional power analysis at the interim analysis stage. Since the futility boundary is assumed non-binding, even it is crossed, the DSMB will make recommendation on whether or to stop the trial taking in consideration the totality of accumulated evidence, including the patient accrual rate, observed treatment effect, etc. The whole evaluation will be conducted in a blinded manner.

Figure 1. Group sequential plot

Two interim analyses were performed as per the protocol. No stopping rules were triggered and the DSMB recommended continuing at each analysis. Therefore, the trial proceeded and

finished.

Analysis Populations

Intention-to-Treat (ITT) population: All randomized patients having at least some outcome data will be included in the analysis in the groups to which they were randomized, regardless of the care they received.

Per-Protocol (PP) population: This analysis includes patients, as long as they have outcome data, who completed the study in accordance with the protocol. The patient in the intervention group is determined to have received the intended intervention if their NIRS measurements during the intervention time window are within 90-110% of the baseline value for 80% of the time. The purpose is to assess the effect of the intervention under optimal conditions.

[figure not shown]
Documentation of Deviations:

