- All protocol deviations will be documented in a protocol deviation log, which will be reviewed regularly by the trial steering committee to ensure consistency in applying the exclusion criteria.
- The rationale for excluding each participant will be documented in detail.

The primary analyses of the primary and secondary outcomes will be based on the ITT population. The per-protocol population will be used in the safety and sensitivity analysis.

Note: Patients who were randomized and treated, but lost to follow up, will be included to the time of dropout. Patients who withdrew their consent to participate the study will not be included in analysis.

The CONSORT diagram as of January 26, 2024 is presented as follows. The last patient was recruited on December 27, 2023. At the time of formulating this statistical analysis plan, the follow-up per research protocol is ongoing. We anticipated to finish patient follow-up in early February 2024.

We will evaluate the baseline homogeneity using absolute standardized differences. For both primary and secondary analyses, we will correct for baseline factors with ASDs above the threshold determined by the following equation: $1.96 \times \sqrt{(\text{nt} + \text{nc})/(\text{nt} * \text{nc})}$.1 where t is treatment and c is control.

Analysis of the primary outcome

The primary outcome will be evaluated using logistic regression to estimate the odds of postoperative composite complications. A one-sided Z-value < -1.932 will be considered statistically significant.

A sensitivity analysis evaluating an average relative effects model. (Edward J Mascha, Daniel I Sessler. Statistical grand rounds: design and analysis of studies with binary- event composite endpoints: guidelines for anesthesia research. *Anesth Analg*. 2011 Jun;112(6):1461-71. doi: 10.1213/ANE.0b013e31821796d3.)

Analysis of the secondary outcomes

For the secondary analysis of continuous and categorical outcomes in the BOTTOMLINE-CS trial, the following details will outline the statistical methods that will be used. All analyses will be adjusted for unbalanced baseline characteristics and reported with 95% confidence intervals.

- Continuous outcomes will be analyzed using linear regression or generalized linear models as appropriate, depending on the distribution of the data and the study design.
- Composite secondary outcomes will be analyzed using the same approach as the primary outcome.

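### Table 1 is a two-sided 0.05 design, but the efficacy and final-significance rules use only its lower tail while quoting the two-tailed alphas, and no numeric rule covers the upper bounds

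*SAP*

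**What the plan says.** Under Sample Size Determination the SAP describes the design thus: "Based on one-sided Z-test group sequential testing with 3 stages (two interim analyses"). It uses "non-binding beta spending (futility) functions", and the planned number "will provide 80% power for detecting a 6% absolute reduction from 30% to 24% at a target alpha-level of 0.05".

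Under Interim Analysis, Table 1 gives, at 309, 618 and 927 patients per arm, efficacy bounds of ±3.710, ±2.511 and ±1.932. Alpha spent is 0.0002, 0.0119 and 0.0379, which sums to 0.0500. The futility bound at stage 2 is ±1.157.

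The rules that use these bounds name one side only. For the first look: "The trial could be stopped for efficacy if the efficacy boundary is crossed at first ($Z < -3.71$, $\alpha < 0.0002". The second look uses Z < -2.51 with an alpha of 0.0119. Under Analysis of the primary outcome: "A one-sided Z-value < -1.932 will be considered statistically significant".

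For a result in the other direction the SAP offers three things, none with a number: continuation after the second look is conditional on there being no concern about safety, the DSMB has discretion over a crossed futility bound, and the DMEC reviews adverse events (Safety Measures).

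On the two looks already done, the SAP reports: "No stopping rules were triggered and the DSMB recommended continuing at each analysis".

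**The concern.** Table and text describe different tests. A reader of the ± table would take it that both directions are tested and that both were checked at each look. A reader of the text would find that only fewer complications under guided care can lead to a conclusion. The alphas quoted beside the one-tailed rules are the two-tailed figures.

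The unused side matters here because the primary outcome also carries much of the trial's safety information. The composite contains death, stroke, cardiac arrest and sepsis, while SAE reporting leaves out typical surgical complications. If the composite went the wrong way, the SAP would have no defined inferential status for the result. The report on the interim looks gives assurance only about the bounds that were actually compared with Z, and the text names only the lower ones.

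**Working it through.** **Inputs (SAP, Sample Size Determination and Table 1).** Looks at 309, 618 and 927 per arm, so information fractions t = 1/3, 2/3 and 1; 30% versus 24%; O'Brien-Fleming-type spending; bounds and alphas as printed.

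**1. Reproduce Table 1's alpha column.** Spending function per tail: α(t) = 2[1 − Φ(z₁₋ₐ/₂ / √t)].
- With a = 0.025 per tail, cumulative spending is 0.000104, 0.006048 and 0.025. The increments are 0.000104, 0.005945 and 0.018952.
- Doubled for two tails: 0.00021, 0.01189 and 0.03790. Table 1 prints 0.0002, 0.0119 and 0.0379.
- The bounds from 0.025 per tail are 3.710 and 2.511, again as printed.
- A one-sided 0.05 design would have bounds of 3.200, 2.141 and 1.695.

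Table 1 is therefore a two-sided 0.05 design.

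**2. Alpha under the text's one-tailed rules.**
- First look: P(Z < −3.71) = 0.0001, against 0.0002 quoted.
- Second look: 0.00595 newly spent, about 0.0060, against 0.0119 quoted.
- All three looks: 0.0250 if futility at 1.157 is obeyed, 0.0284 if it is ignored. The stated one-sided target is 0.05.

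**3. Total error if both tails are used at ±3.710, ±2.511, ±1.932.**
- Futility binding: 2 × 0.0250 = 0.0500.
- Futility non-binding, as the SAP states: 2 × 0.02835 = 0.0567.
- Without futility, the final bound that holds 0.05 would be 1.993.

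**4. What an upper crossing means in patients.** Solve Z = (p − 0.30) / √[2p̄(1 − p̄)/n], with p̄ = (p + 0.30)/2. The control rate of 30% is the SAP's assumption.
- Second look, n = 618, Z = +2.511: p = 0.367, an excess of 6.7 points (about 42 patients).
- Final, n = 927, Z = +1.932: p = 0.342, p̄ = 0.321, standard error 0.0217, an excess of 4.2 points (0.0419 × 927 ≈ 39 patients).
- Final, n = 927, Z = +3: p = 0.366, p̄ = 0.333, standard error 0.0219, an excess of 6.6 points (0.0657 × 927 ≈ 61 patients).

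**5. How often the unused tail would matter.** Take a harm that mirrors the design effect (drift +2.916 at full information). The upper bounds would be crossed with probability 0.021 by the first look, 0.449 by the second and 0.81 overall with binding futility (0.84 without). This scenario is hypothetical. The text's lower-tail rules classify none of these crossings.

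**The case against.** A declared one-sided superiority test need not declare harm, and the SAP does call the test one-sided. That stands. It follows that the absence of a harm claim is not in itself an error. But a one-sided test does not go with ± bounds and two-tailed alphas, so one or the other must be corrected.

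A reader might infer that every rule in the text ignores the upper side. That is not so: the futility interval, −1.16 to 1.16, is symmetric. Its sentence is also ambiguous. On one reading the interval is the futility region, and a Z of +2.8 lies beyond it with no rule attached. On the other it is the region in which the bound is not crossed; then +2.8 counts as crossed and goes to the DSMB, which weighs the observed effect. So it cannot be said that a large positive Z would have led to no action.

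A reader might also infer that the interim looks had no protection against harm. The documents do not support that. The safety proviso and the DMEC review exist, the group sequential plot is not shown, and numeric guidance may stand in the protocol or a DSMB charter. The supported statement is that this SAP gives no numeric rule.

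Nor is it right that the trial could not show harm. The SAP plans an odds ratio with a 95% confidence interval. In the Z = +3 example the odds ratio is (0.366/0.634)/(0.30/0.70) ≈ 1.35, with an interval of about 1.11 to 1.63. The direction would be visible; what is undefined is how the result would be classed.

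**Conclusion.** The point holds as an inconsistency of sidedness. Table 1 spends 0.05 over two tails; the efficacy and final rules use one tail and quote alphas about twice what that tail spends. At the final analysis, a Z above +1.932 (about 4.2 points of excess at a 30% control rate) would be classed as not significant although the table allots alpha to it.

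The interim part is now a matter of reporting, since both looks were complete when the SAP was written. The final rule was still open, because follow-up was under way. The alpha figures assume equally spaced looks, as Table 1's sample sizes imply. The excesses in patients also assume the SAP's 30% control rate.

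**What to change.** Before the final analysis, make Table 1 and the text agree on sidedness in one of two ways.

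- **Two-sided.** State that the primary test is two-sided on Table 1's ± bounds. In Analysis of the primary outcome, add that a final Z above the upper bound, equal in size to the final efficacy bound, will be reported as a statistically significant excess of complications. State alongside it that total type I error at ±1.932 is 0.05 only with binding futility and about 0.057 with non-binding futility as planned. Do not describe the added tail as already covered by Table 1's alpha.
- **One-sided.** Remove the ±, give the one-tailed alpha spent (about 0.0001 and 0.0060 at the two looks), and correct the stated 0.05 target, since the total is 0.025 to 0.028.

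In either case, report the signed Z at both completed looks, and limit the statement that no stopping rule was triggered to the bounds actually checked. Do not relabel the interim efficacy bounds as prespecified harm bounds after the fact.

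The cost is SAP wording and two reported values. No patients are added and the efficacy threshold need not move.

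### The second-interim futility sentence contradicts Table 1: it labels -1.16 < Z < 1.16 as not crossed, although that interval lies inside the futility region

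*SAP*

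**What the plan says.** The SAP's Interim Analysis section reproduces text from the original protocol.

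- **Meaning of futility.** The paragraph that introduces Table 1 describes nominal levels to reject the null for efficacy or to "fail to reject the null hypothesis for futility are calculated as follows". Futility therefore means failing to reject.
- **Table 1.** Stage 2 (618 per group) has efficacy bounds of ±2.511 and futility bounds of ±1.157. At the final stage (927 per group) both are ±1.932. Stated power is 0.803.
- **Direction.** Efficacy at the second interim is Z < -2.51, and the final test under Analysis of the primary outcome is Z < -1.932. Negative Z is benefit.
- **The rule in words.** "If the futility boundary is not crossed ($-1.16 < Z < 1.16$) at second interim analysis, and the study will continue", provided there is no safety concern. If the boundary is crossed, the DSMB advises on stopping from all the evidence, because the boundary is non-binding. Sample Size Determination also refers to "non-binding beta spending (futility) functions".
- **What happened.** "No stopping rules were triggered and the DSMB recommended continuing at each analysis".

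**The concern.** The only sentence that gives the futility limits in words attaches the inner interval to the wrong label. A second-interim Z of 0 would count as futility not crossed. A promising Z of -2.0, short of efficacy, would count as crossed.

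The label has two uses. It decides when the DSMB is asked to weigh stopping for futility. It is also the yardstick for the SAP's report that no stopping rule was triggered. With a second-interim Z near zero, that report would be correct under the sentence, while under Table 1 the futility boundary would have been crossed. A reader cannot tell which is meant.

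**Working it through.** **Inputs.** Event rates are 30% and 24% (Sample Size Determination). The numbers per group are 618 at stage 2 and 927 at the final stage, and the bounds are 3.710, 2.511 and 1.932 for efficacy and 1.157 for stage 2 futility (Table 1). Information fractions are taken as 1/3, 2/3 and 1. No futility stop is assumed at stage 1, where Table 1 shows zero beta spent.

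**Step 1: which region does Table 1 imply?** The final-stage drift is 0.06/√(0.27 × 0.73 × 2/927) = 2.910 with pooled variance, or 0.06/√((0.24 × 0.76 + 0.30 × 0.70)/927) = 2.916 unpooled. Integrating the three-stage design numerically gives:

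| Stage 2 rule | Power at 30% vs 24% | Stated |
|---|---|---|
| Stop for futility if -1.157 < Z < 1.157 | 0.808 to 0.810 | 0.803 |
| Stop for futility if Z > -1.157 (one-sided) | 0.808 to 0.810 | 0.803 |
| No futility stop | 0.839 to 0.840 | 0.803 |
| Continue only inside the interval, unless efficacy is met | 0.476 (pooled) | 0.803 |

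The readings with Z near zero as futile come close to the stated power. The last row is a test of which region the table was built on. It is not a description of how the trial would run, because a non-binding boundary forces no stop.

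The split of beta in Table 1 (0.0828, then 0.1172) was not reproduced. The inner region gives about 0.111 at stage 2 and 0.080 at the final stage. The inverted region would spend about 0.443 at stage 2, which is much further from the table.

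**Step 2: how often is the label wrong?** At 618 per group, SE = √((0.24 × 0.76 + 0.30 × 0.70)/618) = 0.0252, so the mean Z at the design effect is -0.06/0.0252 = -2.381 (-2.376 with pooled variance). Normal probabilities at the second look, taken on its own:

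| Second-interim Z | No effect | Design effect | Sentence, literally | Table 1, one-sided |
|---|---|---|---|---|
| Z < -2.511 | 0.006 | 0.446 to 0.448 | efficacy | efficacy |
| -2.511 to -1.157 | 0.118 | 0.441 to 0.442 | futility crossed | neither crossed |
| -1.157 to 1.157 | 0.753 | 0.110 to 0.111 | futility not crossed | futility crossed |
| Z > 1.157 | 0.124 | 0.0002 | futility crossed | futility crossed |

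The sentence disagrees with Table 1 in the two middle rows: 0.118 + 0.753 = 0.871 of trials with no effect, and about 0.44 + 0.11 = 0.55 at the design effect.

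**Step 3: does the direction make sense?** Conditional power at the design effect is Φ((-1.932 - m)/√(1/3)), with m = z√(2/3) - 2.910/3.

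- At z = 0: m = -0.970, and conditional power is 0.05.
- At z = -2.0: m = -2.603, and conditional power is 0.88.

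The sentence labels the first as not crossed and the second as crossed.

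**The case against.** **A wording slip.** The sentence is ungrammatical, and its bracket could be meant to describe the boundary rather than the condition of not crossing it. Figure 1, which plots the boundaries, is not available here and may show the right region. This is fair as to intent: Table 1 and the definition of futility give the intended direction. But in the efficacy sentence just before, the bracket defines the crossing condition, so the natural reading of the futility bracket is the wrong one.

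**No operational harm.** The boundary is non-binding, and the DSMB would see the observed effect before advising. Both interims are over and recruitment has ended. This stands, and it limits the point to labelling and reporting. It does not settle whether a crossing occurred.

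**A protocol quotation.** The SAP presents the text as the original protocol's, so it should not be silently rewritten. This stands and shapes the fix.

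A reader might infer two stronger points that the SAP does not support:

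- *That the DSMB applied the inverted rule, or that the trial ran on past a futility crossing.* The SAP gives no second-interim Z and does not say which reading was used. Its statement on stopping rules fits either reading, and also fits the fact that a non-binding boundary compels no stop.
- *That the final critical value or the power is compromised.* The final test is fixed at Z < -1.932 whatever the futility status. With no futility stopping, the one-sided error is 0.028, below the one-sided 0.05 stated in Sample Size Determination. The power of 0.476 in the working assumes a mandatory stop that the SAP rules out.

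**Conclusion.** The contradiction is real. At the second interim the sentence labels as not crossed an interval that Table 1 places in the futility region. This holds whether that region is read as symmetric (|Z| < 1.157) or as one-sided (Z > -1.157), since both contain the interval.

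Taken literally, the sentence labels 75% of no-effect trials and 11% of design-effect trials as not crossed, and labels as crossed the 44% of design-effect trials that fall between the two bounds. These are frequencies of a wrong label on an advisory boundary. They are not rates of wrong stopping or wrong continuation, and nothing in the final analysis changes. What remains open is what the report that no stopping rule was triggered means for futility.

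The conclusion rests on Table 1, the SAP's own definition of futility and the power check. The sizes assume the design event rates and 618 per group at the second look.

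**What to change.** 1. Leave the protocol quotation as it stands and add a correcting note to the SAP: *For the one-sided benefit test, the non-binding futility boundary at the second interim is crossed when Z > -1.157, which includes Z >= 1.157. The efficacy boundary is crossed when Z < -2.511. Neither is crossed when -2.511 <= Z <= -1.157.* This leaves no value of Z unclassified.
2. Look up the second-interim Z in the DSMB record, and which reading of the boundary was applied.
3. Replace the statement that no stopping rule was triggered with two: whether the efficacy boundary was crossed at each look, and whether the non-binding futility boundary was crossed at the second. If futility was crossed and the DSMB advised continuing, say so.

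The cost is a short note, a look-up in existing records and one reworded sentence. No new data, patients or analyses are needed.

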- Categorical outcomes will be analyzed using logistic regression for binary outcomes or chi-squared tests for categorical variables with more than two categories.
- Bonferroni-Holm's method will be used for multiplicity adjustment for the p values of those secondary outcomes.

Safety analysis

- This analysis will list all adverse events and serious adverse events that were related to the research procedures.
- The analysis will include rows for each type of adverse event and columns for the intervention group, control group, number of events, percentages, and a comparison column if appropriate.

Sensitivity Analysis

Patients who withdrew from the trial voluntarily will not be included in analysis.

In the sensitivity analyses, we will assess the robustness of the trial findings. These analyses deal with the patients who did not have outcome data and the per-protocol population instead of ITT population. The plan for conducting sensitivity analyses in the BOTTOMLINE-CS trial are outlined as follows:

Missing Data:

- In the analyses of the primary and secondary outcomes as detailed above, we will exclude patients without outcome data. This approach corresponds to missing completely at random (MCAR).
- Under the missing at random (MAR) assumption, we will use Markov Chain Monte Carlo (MCMC) for multiple imputation approach with 20 imputed copies. Standard multiple imputation methods will be adopted.
- Under the missing not at random (MNAR) assumption, we will use the following methods.
 - Best-case and worst-case scenario analysis: For binary outcomes, we will impute all missing outcomes as successes in the intervention group and failures in the control group for the best-case scenario and the opposite for the worst-case scenario.
 - Pattern-mixture models: These models will be used to explore the impact of different missing data patterns on the results.
 - Selection models: We will fit models that make specific assumptions about the mechanism of missingness, such as logistic regression models that include a term for whether data are missing or observed.

Analysis based on the per-protocol population

The above specified analyses for the primary and secondary outcomes will be repeated using the per-protocol population.

Reporting of Sensitivity Analyses:

- Results will be reported focusing any changes in significance or the magnitude of the treatment effect compared to the results of the primary analyses specified above.

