- A narrative will be provided to explain the implications of the sensitivity analyses findings in the context of the trial conclusions.

Subgroup Analyses

- The outcomes targeted in the subgroup analyses include all primary and secondary outcomes. Interactions between the intervention and primary outcome will be evaluated for each subgroup. Odds ratio for the primary outcome, as a function of subgroup, will be presented as a forest plot with 95% confidence intervals.
- The subgroup analyses will be based on the following variables:
 - Age (< 65 years vs. \geq 65 years)
 - Sex (male vs. female)
 - BMI (< 30 kg/m² vs. $>$ 30 kg/m²)
 - Blood component transfusion during the study period (yes vs. no)
 - Duration of surgery (< 3 hours vs. $>$ 3 hours)
 - Temperature during surgery (based on each patient's median value, $<$ 35.5 °C vs. $>$ 35.5 °C)
 - Cerebral tissue oxygen saturation (based on each patient's median value, $<$ 70% vs. $>/=$ 70%)
 - Somatic tissue oxygen saturation (based on each patient's median value, $<$ 75% vs. $>/=$ 75%)
 - Cardiac output index (based on each patient's median value, $<$ 3 L/min/m² vs. $>/=$ 3 L/min/m²)
 - Systemic vascular resistance (based on each patient's median value, $<$ 1000 dyn·s·cm⁻⁵ vs. $>/=$ 1000 dyn·s·cm⁻⁵)
 - Heart rate (based on each patient's median value, $<$ 60 bpm vs. $>/=$ 60 bpm)
 - Mean arterial pressure (based on each patient's median value, $<$ 65 mmHg vs. $>/=$ 65 mmHg)
 - End-tidal carbon dioxide (based on each patient's median value, $<$ 30 mmHg vs. $>/=$ 30 mmHg)
 - History of stroke (yes vs. no)
 - History of myocardial infarction (yes vs. no)
 - History of hypertension control (based on pre-operative measurement with the threshold of 140/90 mmHg, (yes vs. no)
 - Antihypertensive medication, (yes vs. no)
 - History of diabetes (based on the preoperative diagnosis, yes vs. no)
 - History of chronic renal disease (based on the preoperative diagnosis, yes vs. no)
 - History of chronic obstructive pulmonary disease (based on the preoperative diagnosis, yes vs. no)
 - Current cigarette smoking (yes vs. no)

Ethical Considerations

The ethical considerations were specified in the protocol registered before the start of the trial.

Quality Control and Data Management

The quality control and data management were specified in the protocol registered before the start of the trial.

Software and Programming

R software (version 4.3.2, R Foundation for Statistical Computing, Australia).

Tables and Figures

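### The per-protocol set screens intervention patients, but not controls, on the saturation they achieved, so the per-protocol efficacy comparison can lean towards benefit when there is no effect

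*SAP*

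**What the plan says.** The Per-Protocol definition under Analysis Populations has two layers. The first covers both arms: "This analysis includes patients, as long as they have outcome data, who completed the study in accordance with the protocol". The second covers one arm: "The patient in the intervention group is determined to have received the intended intervention if their NIRS measurements during the intervention time window are within" a band of 90–110% of baseline, held for 80% of the time. No matching saturation rule is stated for controls. The stated aim is: "The purpose is to assess the effect of the intervention under optimal conditions".

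The same section makes ITT the basis of the primary analyses and gives the per-protocol set a supporting role: "The per-protocol population will be used in the safety and sensitivity analysis". Under Sensitivity Analysis the SAP then says: "The above specified analyses for the primary and secondary outcomes will be repeated using the per-protocol population". These analyses are meant to assess robustness. They are to be reported for changes in significance or effect size against the primary analysis, with a narrative on what they imply for the trial's conclusions. Adjustment is limited to baseline factors whose standardised difference exceeds a threshold.

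**The concern.** The primary objective tests a strategy: care guided by cerebral and somatic saturation. The second layer of the definition asks what saturation the patient reached, which is a response measured after randomisation. A patient monitored and managed exactly as assigned, whose saturation nevertheless stayed out of the band, counts as not having received the intervention. A control with the same instability stays in.

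The SAP's opening rationale is that tissue hypoperfusion leads to complications. On that reasoning, patients who fall out of the band on the low side are at higher risk. Removing them from one arm lowers that arm's event rate whether or not the intervention works. Adjustment for imbalanced baseline factors may recover part of this, but it cannot remove selection caused by instability during surgery.

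At stake is how a null or borderline ITT result would be read beside a favourable per-protocol result. The pair could be taken to mean that the intervention works when targets are met, and this comparison cannot support that.

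**Working it through.** **The plan's own figure.** The SAP gives no figure for the per-protocol analysis. The design inputs used below do reproduce. A three-stage simulation with 927 per arm, 30% vs 24%, efficacy boundaries 3.710 / 2.511 / 1.932 and the stage-2 futility value 1.157 gives power 0.808 to 0.810 when futility stops the trial. Table 1 of the SAP states 0.803.

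**Inputs from the SAP.** Control risk 30% (Sample Size Determination); 927 per group (Interim Analysis, Table 1); final threshold Z < -1.932 (Analysis of the primary outcome).

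**Assumed inputs.** Share *a* of intervention patients in target, and the odds ratio *OR* of the composite for higher-risk non-attainers against attainers. The SAP gives neither. There is no true effect, so the whole intervention arm has 30% risk. Exclusions under the general protocol-completion condition, covariate adjustment and the interim looks are not modelled.

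**Step 1: risk in attainers, p.** If every non-attainer carries the excess risk, solve

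a·p + (1 − a)·OR·p / (1 − p + OR·p) = 0.30.

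For a = 0.8 and OR = 2, p = 0.2690 and the non-attainer risk is 0.538/1.269 = 0.424. Check: 0.8 × 0.2690 + 0.2 × 0.424 = 0.300.

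**Step 2: expected Z of attainers against controls.**

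SE = √[p(1 − p)/(927a) + 0.21/927] = √[0.269 × 0.731/741.6 + 0.21/927] = 0.0222.

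Z = (0.2690 − 0.30)/0.0222 = −1.40.

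**Step 3: chance of crossing.** Φ(−1.932 + 1.40) ≈ 0.30. With no selection it is Φ(−1.932) = 0.027.

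**Step 4: allow for the two-sided band.** The rule also drops patients above 110% of baseline, who need not be at higher risk. Suppose half of the non-attainers carry the excess odds and half have the attainers' risk. Step 1 becomes

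[a + (1 − a)/2]·p + [(1 − a)/2]·OR·p / (1 − p + OR·p) = 0.30.

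For a = 0.8 and OR = 2, p = 0.2842, SE = 0.0224, Z = −0.71 and the chance of crossing is 11%.

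| Attain | OR | All non-attainers at excess risk | Half at excess risk |
|---|---|---|---|
| 90% | 1.5 | 29.1% vs 30%; 6% cross | 29.5% vs 30%; 4% cross |
| 80% | 2 | 26.9% vs 30%; 30% cross | 28.4% vs 30%; 11% cross |
| 70% | 2.5 | 24.0% vs 30%; 77% cross | 26.8% vs 30%; 29% cross |

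A log-odds-ratio version of steps 2 and 3, closer to the planned logistic model, gives 6.4% for the first row and 29.4% for the second (per-protocol odds ratio 0.86), with all non-attainers at excess risk. Over a wider grid (attainment 50–90%, OR 1.25–3, all non-attainers at excess risk) the spurious difference runs from −0.5 to −11.1 percentage points and the chance of crossing from 4.4% to 99%. At OR = 1 there is no bias.

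**The case against.** The strongest reply is that this is a declared sensitivity analysis beside a primary ITT analysis, with a numerical rule that does not use clinical outcome and an openly stated aim of looking at optimal conditions. Much of that stands, and it rules out several stronger readings.

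- A reader might infer that target attainers are compared with every control. They are not: "who completed the study in accordance with the protocol" governs both arms, and the SAP requires a deviation log with a documented reason for each exclusion. Only the saturation criterion is one-sided.
- A reader might infer that delivery of care is ignored altogether. The general condition may cover part of it, and the detail may sit in the protocol, which is not at hand. The defect is that achieved saturation is added on top, in one arm.
- A reader might infer a false-positive trial. The threshold of -1.932 governs the primary ITT test. A crossing in the per-protocol set changes no primary conclusion.
- A reader might take one line of the table as the expected bias. The inputs are assumed, and they matter: allowing for patients above the band cuts 30% to 11% in the middle scenario.
- Keeping a monitored patient who stayed stable and needed no action is not misclassification. That patient may well have received the assigned strategy.

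What does not stand is the appeal to optimal conditions. Removing non-attainers from one arm while comparable controls remain does not estimate the effect under good adherence. A check that can lean towards benefit is also a poor test of robustness. Applying the same saturation filter to controls would remove the asymmetry, but it would condition on the intervention's own effect if the intervention changes saturation.

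**Conclusion.** The point holds as a flaw in a sensitivity analysis. As written, the per-protocol efficacy comparison selects on a post-randomisation response in the intervention arm only. It leans towards benefit whenever patients who stay in the band have the better prognosis, which the trial's own rationale makes plausible. That the rule is one-sided is clear from the text; how large the bias is cannot be known from it. In the three scenarios the spurious difference runs from about half a percentage point to 6 points, the full design effect. The chance of crossing -1.932 runs from 4% to 77%, against 2.7% without selection. There is no bias if attainers and non-attainers share the same prognosis. The ITT analysis and the primary conclusion are unaffected.

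**What to change.** Define the per-protocol set by delivery of the assigned care, with criteria judged in both arms: monitored and managed as assigned, no crossover, and no major deviation in the deviation log. Drop achieved saturation as a membership criterion. Report attainment of the 90–110% / 80% target as a descriptive adherence table, by arm if control traces exist. The subgroup list suggests they may, since it uses "Cerebral tissue oxygen saturation (based on each patient's median value" without limiting it to one arm.

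Recruitment has ended, and the SAP does not show that adherence to the care algorithm was recorded. If the records are not sufficient, keep the attainment-based comparison as descriptive only, and state that it is neither a causal estimate nor a robustness check.

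An instrumental-variable estimate for target attainment should not be used unless the assumption that assignment acts only through attainment is stated and defended. It fails if guided care helps patients who still miss the target.

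Cost: a change of SAP wording and one population flag re-derived from the deviation log and care records, which is more work if those records are thin. The per-protocol effect may look less favourable. The ITT analysis does not change.
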